16.0 DATA COLLECTION

All required data for this investigation are to be collected on standardized electronic case report forms (eCRFs) for individual enrolled subjects; sample eCRFs are provided. The eCRF must be electronically signed by the Principal Investigator or co-Investigator listed in the Clinical Studies Agreement and/or Delegation of Authority Log. If for any reason the eCRFs are unavailable and/or inaccessible, paper CRFs will be provided by the Sponsor to be completed, signed by the Principal Investigator or designee and submitted to the Sponsor.

Confidential

Case Report Form Instructions will be provided to assist the Investigator(s) and appropriate investigational staff in the completion of the required eCRFs. Source documents are original documents, data, and records from which the subject's CRF data are obtained. These include, but are not limited to, hospital records, clinical and office charts, laboratory records, and correspondence. Electronic CRFs must be kept current to reflect enrolled subject status during the course of the investigation.

17.0 IMAGING CORE LAB

All baseline and follow-up transthoracic echocardiograms, transesophageal echocardiograms and CT scans will be evaluated at The Baylor Scott & White Research Institute Imaging Core Lab, under the direction of [name] and [name] M.D.

Follow-up Doppler echocardiograms will be evaluated by the designated Echo Core Lab. A standardized written report generated by the Core Lab for each Doppler echocardiogram will be entered into an electronic database maintained by the Sponsor. The Clinical Site Manager or Sponsor designee shall notify the Investigator should there be any indication of a complication or discrepancy that the Investigator may not have noted. This will allow Page **17** of **57** or an opportunity to further review the test results and clarify the findings if necessary.

18.0 SCREENING/ENROLLMENT LOG

All subjects considered for the study will be recorded on the Screening Log. A Screening Log will be provided to the investigational sites to maintain a cumulative log of all screened subjects. For subjects who are ineligible for participation in the clinical investigation, a reason supporting the disqualification of the subject must be entered on the Screening Log.

19.0 DEVIATIONS FROM THE STUDY PROTOCOL

The Investigator will not deviate from the protocol without the prior written approval of the Sponsor except in medical emergencies or in unforeseen, isolated instances where minor changes are made that will not increase the subject's risk or affect the validity of the study. Any subsequent revisions to the

Confidential

protocol, including the Informed Consent Form and the Case Report Forms, other than very minor revisions, must be approved by the Sponsor, the FDA, and the IRB. In medical emergencies, prior approval for protocol deviations will not be required, but the Sponsor or its designee and IRB must be notified within 5 working days of the incident. Periodic monitoring of protocol compliance will be performed for each site. Deviations will be documented on the appropriate case report form. The sponsor has the right to suspend enrollment at sites deemed to have excessive protocol compliance issues.

20.0 INVESTIGATOR RESPONSIBILITIES

The Investigator is responsible for ensuring that this clinical study is conducted according to the Investigator Agreement, Protocol, all conditions of FDA and IRB approval and applicable FDA regulations. Written IRB approval of the protocol and ICF must be provided to the Sponsor prior to the enrollment of any subject in the clinical study at each investigational site. The Investigator is responsible for ensuring that informed consent is obtained from all subjects prior to any diagnostic tests or treatments that are outside the standard course of treatment that would be followed if this subject was not being considered for enrollment in this clinical study. Subjects must be informed that their medical records will be subject to review by the Sponsor, its authorized designee or representatives of FDA. Subjects will be informed that they are free to refuse participation in this clinical study without loss of benefits to which they are otherwise entitled, and, that if they choose to participate, they may withdraw at any time without prejudice to future care. The informed consent provided by each investigational site's IRB must be signed prior to study participation. The original signed informed consent for each subject must be retained by the Investigator and is subject to review by the Sponsor and the FDA. A copy of the informed consent will be provided to the subject.

21.0 WITHDRAWAL

Subjects may voluntarily withdraw from the study at any time. If such withdrawal occurs, or if the subject fails to return for visits, the site investigator must determine the primary reason for a subject's premature withdrawal from the study and record this information in the subject's study records.

For subjects who are lost to follow-up, the site investigator should show "due diligence" by documenting in the subject record steps taken to contact the subject, e.g., dates of telephone calls, registered letters, etc.

Subjects who are prematurely withdrawn from study treatment or from the study will not be replaced.

22.1 POTENTIAL RISKS AND BENEFITS

The risks associated with the use of the system are similar to those encountered with standard cardiac catheterization, use of anesthesia, mitral valve replacement (MVR) and the use of bioprosthetic heart valves, in addition to risks associated with study-related procedures (e.g. Transesophageal echocardiography, MSCT scan, etc.). A list of anticipated or potential adverse events is provided below.

22.2 Adverse Events

An adverse event is any undesirable clinical occurrence in a study subject, whether or not it is related to the study intervention. Any condition that was recorded as pre-existing is *not* an AE unless there is a change in the nature, severity or degree of the condition. Furthermore, for a pre-existing condition that is not protocol defined to be reported as an adverse event, a change in severity must meet the criteria for being serious (see definition below).

22.3 Serious Adverse Event

Serious adverse events are defined by FDA regulation as any experience that results in a fatality or is life threatening; results in significant or persistent disability; requires or prolongs a hospitalization; results in a congenital anomaly/birth defect; or represents other significant hazards or potentially serious harm to research subjects or others, in the opinion of the investigators. Important medical events that may not result in death, be life-threatening, or require hospitalization may be considered a serious adverse event when, based upon appropriate medical judgment, they may jeopardize the subject and may require medical or surgical intervention to prevent one of the outcomes listed in this definition.

22.4 Unanticipated Serious Adverse Event

An unanticipated (unexpected) serious adverse event is any serious adverse event that is not protocol-defined. Expedited reporting is required for serious adverse events that are unexpected.

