22.5 Event Recording

The following adverse events will be captured throughout the period of study participation:

- A. Protocol-defined (as described below)
- B. Serious unanticipated events (serious "Other" adverse events)

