22.7 Reporting of Serious Adverse Events

All investigators must report both expected (protocol-defined) and unexpected serious adverse events. All serious protocol defined adverse events must be reported directly to the clinical center's IRB and the sponsor within 10 working days of knowledge of the event, or as dictated by the specific IRB policy, whichever is sooner. All unexpected serious adverse events must be reported to the sponsor within 24 hours of knowledge of the event and the clinical center's IRB as dictated by the specific IRB policy.

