22.9 Anticipated or Potential Adverse Events

The list below provides anticipated or potential adverse events that may occur during the study. The potential adverse events are those that are expected to occur during the study because they are associated with the surgical procedure, stress-induced tests (e.g. TEE/TOE, TTE, MSCT scan, exercise tolerance, etc.), or the heart failure population over time. It is anticipated that subjects may require temporary medical and/or mechanical hemodynamic support in the peri and/or early post-op period. These events are not considered adverse events.

- Abnormal Lab values
- Allergic Reaction to Anesthetic, Anticoagulant Therapy, Contrast or Cobalt Chromium
- Anaphylactic Shock or Toxic Reaction
- Anemia
- Angina
- Annulus Rupture/ A-V Groove Disruption
- Aortic Valve Impairment/Damage
- Arrhythmias
- Atrial Fibrillation
- Atrio-ventricular Node Block
- A-V fistula or pseudo-aneurysm
- Bleeding diathesis
- Cardiac Arrest
- Cardiac Failure or Decompensation
- Cardiac Perforation
- Cardiac Tamponade/ Pericardial Effusion
- Cardiogenic Shock
- Chordal Rupture

- Conduction System Injury (defect) which may require pacemaker
- Conversion to Open Sternotomy
- Coronary Artery Obstruction
- Death
- Dissection, Any Vessel
- Dyspnea
- Edema
- Electrolyte Imbalance
- Electro-mechanical Dissociation
- Embolization including air, particulate, calcific material, or thrombus
- Emergent PCI
- Emergent Cardiac Surgery
- Endocarditis
- Esophagus Irritation/Perforation (TEE related)
- Fever
- Frame Strut Fracture
- GI Bleeding
- Heart Failure

SITRAL

Baylor Scott & White Research Institute

- Hematoma
- Hemolysis / Hemolytic Anemia
- Hemorrhage require transfusion/surgery
- Infection at the access site
- Inflammation
- Leaflet tearing
- Left Ventricle Failure
- Local and Systemic Infection
- LVOT Obstruction
- Mal-positioning of Prosthesis
- Multi-system Failure
- Myocardial Infarction
- Myocardial Ischemia
- Pacemaker Implantation
- Pannus Formation
- Papillary Muscle Damage
- Peripheral Ischemia
- Pleural effusion
- Pneumonia
- Prosthesis Dislodgement/Embolization
- Prosthesis Leaflet Entrapment

- Prosthesis Migration
- Prosthesis Paravalvular Leak
- Prosthesis Regurgitation
- Prosthetic Valvular Endocarditis
- Prosthetic Valvular Thrombosis
- Pulmonary Edema
- Pulmonary Vein Obstruction
- Reintervention or reoperation
- Renal Failure or Insufficiency
- Respiratory Failure
- Retroperitoneal Bleed
- Septicemia

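### The 24-hour sponsor notice excludes protocol-defined SAEs, so death, annular rupture, prosthesis embolization and (on the natural reading) stroke may be reported up to 10 working days later

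*Combined protocol and SAP*

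**What the plan says.** The reporting rule is spread over several parts of Section 22 of the protocol.

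- **22.4** defines an unexpected SAE as "any serious adverse event that is not protocol-defined", and then sets the consequence: "Expedited reporting is required for serious adverse events that are unexpected".
- **22.5** says which events are captured. The first category is "Protocol-defined (as described below"), with no section or table named.
- **22.7** sets two clocks. For unexpected events, "All unexpected serious adverse events must be reported to the sponsor within 24 hours of knowledge of the event". Serious protocol-defined events, which the section treats as the expected ones, go to the "IRB and the sponsor within 10 working days of knowledge of the event, or as dictated by the specific IRB policy, whichever is sooner".
- **22.9, Anticipated or Potential Adverse Events**, is the only event list that follows 22.5 within Section 22. It includes "Annulus Rupture/ A-V Groove Disruption", death, prosthesis dislodgement or embolization, and stroke. It also names cardiac arrest, LVOT obstruction, conversion to open sternotomy and emergent cardiac surgery.
- **Table 1.0** (also numbered 22.9) asks for SAE reports immediately. Its outer limit gives the number 10 followed by both days and hours as units. It has no separate 24-hour row and allows 10 working days for an unanticipated adverse device effect.

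Section 6.1 makes technical, device and procedural success the primary safety endpoints. Section 15.0 has the DSMB review events periodically and charges it with assuring that subjects are not exposed to unreasonable risk.

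**The concern.** Whether an SAE gets the fast clock depends on whether it was foreseen, not on how grave it is. The foreseen events include those that decide the primary safety endpoints. A site can report a procedural death or an annular rupture on the ninth working day and still comply with Section 22.7, while a milder but unlisted SAE must be reported within 24 hours.

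This is a multi-centre feasibility study of a new use of the valve. Section 1.0 motivates it by mortality, LVOT obstruction and embolization seen with an earlier approach. What matters is whether the sponsor, and through it the DSMB, learns of such an event at one centre before another centre operates. The protocol describes no event-triggered notice to the DSMB.

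**Working it through.** The plan gives no figure to reproduce here: Section 4.0 states only a maximum of 30 subjects, and Section 23.0 is descriptive. The check is mainly a trace through the text.

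**Step 1. Trace the four events.**

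| Event | Failure under 6.1 | On the 22.9 anticipated list | In Appendix 2 | Sponsor clock in 22.7 |
|---|---|---|---|---|
| Death | Technical, device and procedural success | Yes | Yes (mortality definitions) | 10 working days on either list |
| Annulus rupture | Device and procedural success | Yes | Yes (major vascular complications) | 10 working days on either list |
| Prosthesis embolization | Device and procedural success | Yes | Yes (device malpositioning) | 10 working days on either list |
| Stroke | Device and procedural success | Yes | No definition in the available text | 10 working days on the 22.9 list; unclear if Appendix 2 is meant |

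Procedural success includes device success, so each device failure counts in both. On the natural reading, 0 of 4 events reach the 24-hour route. If Appendix 2 is the intended list, three still do not and the fourth is uncertain. In both cases 22.7 allows an earlier report where IRB policy requires it.

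**Step 2. Convert the clock.** Ten working days without holidays is 14 calendar days when the site learns of the event on a weekday, 13 on a Saturday and 12 on a Sunday. The expedited clock is 1 day.

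**Step 3. Look for another route that sets a firm short limit.**

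- Table 1.0 asks for immediate reporting but prints an unreadable limit. It does not reproduce the 24 hours of 22.7.
- The IRB clause in 22.7 varies by site and sets no common limit.
- Remote review of entered data (15.0) depends on data entry. Section 7.0 expects forms within 5 business days and 22.8 within 10 days, which also disagree.
- DSMB review is periodic (15.0).

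None of these gives a firm limit shorter than 5 business days.

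**Step 4. Scale only.** Expected events = n × p; chance of at least one = 1 − (1 − p)^n, with n = 30 (Section 4.0).

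| Rate p | Source | Expected | Chance of at least one |
|---|---|---|---|
| Death 10% | Assumption | 30 × 0.10 = 3.0 | 1 − 0.90^30 = 0.958 |
| Death 20% | Assumption | 30 × 0.20 = 6.0 | 1 − 0.80^30 = 0.999 |
| Death 34% | Section 1.0, different approach | 30 × 0.34 = 10.2 | more than 0.999 |
| Embolization 7% | Section 1.0, different approach | 30 × 0.07 = 2.1 | 1 − 0.93^30 = 0.887 |

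Even at the lowest assumed mortality, at least one death is very likely. None of these deaths would require 24-hour notice, because death is on both candidate lists.

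**The case against.** The strongest reply is that 10 working days is an outer limit, not the expected delay. Table 1.0 asks for every SAE to be reported immediately, listed or not, 22.7 yields to a faster IRB policy, and 15.0 adds remote review of the database. This stands against the inference that the sponsor will in practice wait two weeks, or that the DSMB cannot do its job. The documents support only that prompt awareness is not assured.

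Second, 22.5 does not name its list, so tying it to the anticipated events is an inference. It is well supported, because 22.7 equates expected with protocol-defined and the list is introduced as events expected during the study. Appendix 2 remains possible, and then stroke might qualify for 24-hour notice. The other three events would not.

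Third, a reader might infer that no primary endpoint failure can ever trigger the fast route. That goes too far. Erosion and intubation beyond 48 hours are endpoint components in 6.1 but are not on the anticipated list under those terms.

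Fourth, the 34% mortality comes from a mainly transcatheter experience whose problems this surgical approach hopes to mitigate. It should not be read as a forecast, hence the range. The documents give no accrual rate, so they do not show how many subjects other centres would treat during a reporting lag.

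**Conclusion.** The point holds in bounded form. Sections 22.4 and 22.7 together leave death, annulus rupture and prosthesis embolization outside the 24-hour notice on either candidate list, and stroke outside it on the natural reading. The permitted delay is 12 to 14 calendar days against 1, unless IRB policy is faster. Table 1.0 disagrees with 22.7 and sets no usable limit, and nothing carries an individual event to the DSMB between its periodic reviews.

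The conclusion about the clock rests on the text and needs no event rate. The counts of about 3, 6 or 10 deaths indicate scale only and depend on the assumed mortality. This should be corrected because it concerns subject safety and the remedy is mainly wording.

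**What to change.** 1. In 22.4, 22.7 and Table 1.0, apply the existing 24-hour sponsor notice to every death and to every SAE that fails a component of the primary endpoints in 6.1, whether or not it is listed. Keep it for unexpected SAEs.
2. Keep the 10-working-day rule, with its IRB clause, for other listed SAEs.
3. In 22.5, name the list that is protocol-defined.
4. In Table 1.0, replace the limit that carries two units so that it agrees with 22.7, and reconcile the unanticipated device effect row with the 24-hour rule.
5. In 15.0, state that the sponsor forwards these expedited notices to the DSMB on receipt. Without this, faster site-to-sponsor reporting does not reach the body charged with acting on it.

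The cost is a protocol wording change and a modest number of additional notices. Deaths alone would add about 3 to 10 over the study on the range above, plus non-fatal endpoint-failing SAEs. The documents give no rates for stroke or annular rupture, so a total cannot be calculated. No change to endpoints, sample size or analysis is needed.

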22.5 Event Recording

The following adverse events will be captured throughout the period of study participation:

- A. Protocol-defined (as described below)
- B. Serious unanticipated events (serious "Other" adverse events)

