22.8 Eliciting adverse effect information

Investigators are responsible for preparing and submitting all reports as summarized on Table 1.0.

Case Report Forms should be entered within 10 days after the corresponding visit. Investigators are responsible for notifying the Sponsor of any changes to previously reported data. Upon request of the reviewing IRB, FDA, the Investigator must provide accurate, complete, and current information about any aspect of the study.

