22.9 Table 1.0: Investigator Report Requirements

Report title/description	Requirement(s)	Submit to:
Adverse events (AE)	Immediately but no later than 10 days of becoming aware	Sponsor
Serious Adverse Event (SAE)	Report should be submitted immediately after the Investigator first learns of the event but no longer than 10 days hours	Sponsor If applicable, IRB
Unanticipated Adverse Device Effect (UADE)	Report should be submitted immediately after the Investigator first learns of the event but no longer than 10 working days	Sponsor IRB
Withdrawal of IRB approval	Report must be submitted immediately after the Investigator learns of the withdrawal but no longer than 5 working days.	Sponsor
Progress Report	Report must be submitted annually, or as required by the IRB, for the duration of the clinical study. The Sponsor may also prepare this report.	If applicable, IRB
CIP Deviations	Deviations from the investigational plan must be approved by the Sponsor prior to implementation NOTE: If the deviation affects the scientific soundness of the CIP or the rights, safety or welfare of the Subjects, the deviation must be approved by the Sponsor and IRB, if applicable.	Sponsor If Applicable IRB
	In the event that a CIP deviation occurs and the sponsor cannot be notified ahead of time (e.g., if the notification was to protect the life or physical well-being of the Subject),	Sponsor IRB

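### Section 22.5 and Table 1.0 set different scopes for adverse events, so a non-serious, unlisted event related to the device or procedure may be recorded or not depending on which rule a site follows.

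*Combined protocol and SAP*

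**What the plan says.** Four places in section 22 bear on which adverse events enter the record.

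- **Definition (22.2).** "An adverse event is any undesirable clinical occurrence in a study subject, whether or not it is related to the study intervention". The section makes one exception: for a pre-existing condition that is not protocol-defined, "a change in severity must meet the criteria for being serious".
- **Capture (22.5).** "The following adverse events will be captured throughout the period of study participation", followed by two groups. Group A is "Protocol-defined (as described below"), with no list named. Group B is "Serious unanticipated events".
- **Reporting (Table 1.0).** The row for adverse events gives a deadline, "Immediately but no later than 10 days of becoming aware", and a recipient, the sponsor. It has no condition on seriousness or listing. Serious events and the "Unanticipated Adverse Device Effect (UADE") have rows of their own.
- **Status of the table (22.8).** "Investigators are responsible for preparing and submitting all reports as summarized on Table 1.0".

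Section 22.7 sets reporting rules for serious events only. Section 15.0 asks the DSMB to look periodically at adverse events as well as serious ones. The Table of Events (section 25.0) schedules an adverse-event assessment at the procedure, at discharge and at each follow-up visit, without narrowing its scope.

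**The concern.** Under section 22.5 alone, a site need not record a non-serious event that is not protocol-defined. Under Table 1.0, read with section 22.2, the same site should send that event to the sponsor. Both instructions are current, and nothing ranks one above the other.

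This matters because section 3.0 gives safety and feasibility as the purpose, for a valve placed in the mitral position by a surgical route. Events that nobody listed in advance, including milder ones, are part of what a feasibility study should find. If sites choose different rules, differences in recorded events between centers partly reflect recording practice. If all sites choose section 22.5, an absence of such events in the database says nothing about whether they occurred.

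**Working it through.** The protocol gives no adverse-event rate and no sample-size calculation, so there is no stated figure to reproduce. The main check is to set the two rules side by side.

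**Step 1. Classify events by listing and seriousness.** Section 22.4 makes any serious event that is not protocol-defined an unanticipated serious event, so group B of section 22.5 is that cell.

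| Event | Section 22.5 | Table 1.0 AE row, read with 22.2 |
|---|---|---|
| Protocol-defined, serious | Captured (A) | Covered |
| Protocol-defined, non-serious | Captured (A) | Covered |
| Not protocol-defined, serious | Captured (B) | Covered |
| Not protocol-defined, non-serious | Not captured | Covered |

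The rules differ only in the last row. Within that row, section 22.2 already removes non-serious worsening of a pre-existing condition; what remains is new non-serious events.

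**Step 2. Ask how large the last row is.** That depends on what protocol-defined means.

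- If it means the anticipated-event list (the second section numbered 22.9), the row is small. The list includes abnormal laboratory values, fever, edema, arrhythmias, pleural effusion and most device failure modes. Some procedure-related events are still absent, for example pneumothorax and post-thoracotomy pain.
- If it means the Appendix 2 definitions, the row is larger. Fever, edema and pleural effusion, for instance, have no entry of their own there.

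Section 22.7 treats expected and protocol-defined as the same thing, and the second section 22.9 describes its list as events expected to occur. That favors the broad list but does not settle it.

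**Step 3. Check whether other provisions close the gap.** Section 22.7 is confined to serious events. The remote review in section 15.0 works on data already entered. The unanticipated-device-effect row is a second route, but the term is not defined in the supplied text. The Possible grade in section 22.6 covers events that are not known reactions to the surgery and sets no seriousness condition. A non-serious event of that kind that is also unlisted has no capture route under section 22.5.

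**Step 4. Illustrate the effect on a recorded proportion.** Let p be the true proportion of subjects with such an event and s the share of subjects at sites that follow Table 1.0. Then the expected recorded proportion is p × s. Both inputs are assumptions; neither comes from the documents.

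| Assumed p | Expected subjects, 30 × p | s = 0 | s = 0.5 | s = 1 |
|---|---|---|---|---|
| 5% | 1.5 | 0% | 2.5% | 5% |
| 10% | 3 | 0% | 5% | 10% |
| 20% | 6 | 0% | 10% | 20% |
| 30% | 9 | 0% | 15% | 30% |

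With s = 0 the record shows 0 of 30 whatever p is. Taken at face value, that gives a one-sided upper 95% bound of 1 − 0.05^(1/30) = 9.5%, or 1 − 0.025^(1/30) = 11.6% as the upper limit of a two-sided interval. Neither bound would be valid, because the events were never eligible to be recorded.

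**The case against.** The strongest reply is that the sections do different jobs: section 22.5 sets scope, and Table 1.0 sets timing and addressee for whatever falls within it. Targeted capture is a legitimate choice in a study of up to 30 subjects, and the seriousness threshold in section 22.2 for pre-existing conditions fits it. This reading is possible, but the protocol does not state it. The threshold also cuts the other way: if section 22.5 already left out all non-serious events that are not protocol-defined, a special rule for pre-existing conditions would be unnecessary.

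Several parts of the reply stand.

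- A reader might infer that Table 1.0 expressly demands all adverse events without exception. It does not; the row says adverse events, and the wide scope comes from combining it with section 22.2.
- A reader might infer that device effects in particular will be lost. If the section 22.9 list is meant, few device effects are both unlisted and non-serious. The device-effect row and the wide definition of seriousness in section 22.3 may catch others.
- A reader might want to attach a count of missing events. The documents give no basis for one.
- Section 16.0 provides standardized eCRFs with completion instructions, which may impose one scope in practice. Those instructions are not in the documents, so this can be neither relied on nor ruled out.

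**Conclusion.** The inconsistency is real and minor. Section 22.5 and Table 1.0 disagree about non-serious events that are not protocol-defined, and the set meant by protocol-defined is not identified. Whether a site records such an event when it is related to the device or procedure therefore depends on the rule it follows.

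The number of events is unknown: probably small under the section 22.9 list, larger under Appendix 2. The proportions in the illustration show direction only. Variation between sites is a possibility that the text allows, not something the documents show.

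The effect falls on the adverse-event data that the DSMB reviews and on any adverse-event summary. A reader might infer that the main results are at risk, but the documents do not support that. The components of technical, device and procedural success are specified in section 6.1. Section 23.0 plans descriptive statistics for success outcomes and no adverse-event rate.

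**What to change.** Make three small edits to section 22 so that one scope applies throughout.

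1. In section 22.5, group A, name the list that protocol-defined refers to: the anticipated-event list in section 22.9, Appendix 2, or both.
2. Add a third group to section 22.5: *C. Any other adverse event, serious or not, graded possible or probable under 22.6 in relation to the surgical intervention (surgical procedure or valve implant).* This wording follows section 22.6, which grades causality against the surgical intervention and asks for procedure and implant to be separated only where possible.
3. Change the adverse-event row of Table 1.0 to *adverse events captured under 22.5*.

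A definition of the unanticipated adverse device effect, placed beside section 22.4, would make clear which events that separate row is meant to catch.

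The cost is a few lines of protocol text and a few extra eCRF entries per subject. If the sponsor prefers targeted capture without group C, edits 1 and 3 still remove the contradiction. The protocol should then say openly that non-serious related events outside the list are not recorded.
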